4.1.2 Exclusion Criteria

Patients who meet any of the following criteria will be excluded from study entry:

Disease-Specific Exclusion Criteria

- HER2-positive disease by local laboratory testing (IHC 3+ staining or in situ hybridization positive)
- Prior treatment with fulvestrant
- Prior treatment with a PI3K inhibitor, mTOR inhibitor (such as everolimus), or AKT inhibitor. See [Appendix 5](#) for a comprehensive list of excluded treatments.
- Prior anti-cancer therapy within 2 weeks prior to Cycle 1 Day 1
- Prior radiation therapy within 2 weeks prior to Cycle 1 Day 1
- All acute treatment-related toxicity must have resolved to Grade ≤ 1 or be deemed stable by the investigator
- Prior treatment with > 1 cytotoxic chemotherapy regimen for MBC
- Symptomatic hypercalcemia requiring continued use of bisphosphonate or denosumab therapy
 - Use of bisphosphonate therapy or denosumab for other reasons (e.g., bone metastasis, osteoporosis, etc.) is allowed
- Concurrent hormone replacement therapy
- Known untreated or active CNS metastases (progressing or requiring anticonvulsants or corticosteroids for symptomatic control); a computed tomography (CT) scan or magnetic resonance imaging (MRI) of the brain will be performed at screening if required by the local health authority

Patients with a history of treated CNS metastases are eligible, provided they meet all of the following criteria:

Evaluable or measurable disease per inclusion criteria outside the CNS is present.

Radiographic demonstration of improvement upon the completion of CNS-directed therapy and no evidence of interim progression between the completion of CNS-directed therapy and the screening radiographic study

No history of intracranial hemorrhage or spinal cord hemorrhage

Minimum of 2 weeks between completion of radiotherapy and Cycle 1, Day 1 and recovery from significant (Grade ≥ 3) acute toxicity with no ongoing requirement for ≥ 10 mg of prednisone per day or an equivalent dose of other corticosteroid

- History of other malignancy within the previous 5 years, except for appropriately treated carcinoma in situ of the cervix, non-melanoma skin carcinoma, Stage I uterine cancer, or patients who have undergone potentially curative therapy with no evidence of disease and are deemed by the treating physician to be at low risk for recurrence

General Exclusion Criteria

- Type 1 or Type 2 diabetes mellitus requiring anti-hyperglycemic medications
- Clinically significant cardiac or pulmonary dysfunction, including the following:
 - Current uncontrolled Grade ≥ 2 hypertension or unstable angina
 - Symptomatic congestive heart failure or serious cardiac arrhythmia requiring treatment, with the exceptions of atrial fibrillation and paroxysmal supraventricular tachycardia or a conduction abnormality that has been treated and for which the patient is no longer at risk for serious arrhythmia (e.g., Wolff-Parkinson-White syndrome treated with surgical ablation)
- Current dyspnea at rest or any requirement for supplemental oxygen therapy to perform activities of daily living
- History of malabsorption syndrome or other condition that would interfere with enteral absorption
- Inability or unwillingness to swallow pills or receive intramuscular injections
- Clinically significant history of liver disease, including cirrhosis, current alcohol abuse, or current known active infection with HIV, hepatitis B virus (HBV), or hepatitis C virus (HCV)

Active infection is defined as requiring treatment with antiviral therapy or presence of positive test results for hepatitis B (hepatitis B surface antigen and/or total hepatitis B core antibody) or HCV antibody. Unless required by local regulations, patients are not required to have HIV, HBV, or HCV assessments at screening if these assessments have not been previously performed.

Patients who test positive for hepatitis B core antibody are eligible only if test results are also positive for hepatitis B surface antibody and polymerase chain reaction (PCR) is negative for HBV DNA.

Patients who are positive for HCV serology are only eligible if testing for HCV RNA is negative.

- History of inflammatory bowel disease (e.g., Crohn's disease or ulcerative colitis)
- Active bowel inflammation (e.g., diverticulitis)
- Immunocompromised status due to current known active infection with HIV or because of the use of immunosuppressive therapies for other conditions
- Need for current chronic corticosteroid therapy (≥ 10 mg of prednisone per day or an equivalent dose of other anti-inflammatory corticosteroids)

Stable use (i.e., no change in dose within 3 months prior to Cycle 1 Day 1) of inhaled corticosteroids is allowed.

- Pregnancy, lactation, or breastfeeding
- Current severe, uncontrolled systemic disease (e.g., clinically significant cardiovascular, pulmonary, or metabolic or infectious disease)
- Major surgical procedure or significant traumatic injury within 28 days prior to Cycle 1, Day 1 or anticipation of the need for major surgery during the course of study treatment
- Inability to comply with study and follow-up procedures
- Inability to understand the local language(s) for which the EORTC QLQ-C30, the modified Breast Cancer module QLQ-BR23, and the EQ-5D questionnaires are available (see [Appendix 7](#), [Appendix 8](#), and [Appendix 9](#)).

4.2 METHOD OF TREATMENT ASSIGNMENT AND BLINDING

After written informed consent has been obtained and eligibility has been established and approved, the study site will obtain the patient's identification number and treatment assignment from the interactive voice/Web response system (IxRS). Patients will be randomized to receive either taselisib + fulvestrant or the placebo + fulvestrant on the basis of a 2:1 randomization ratio. Patients with *PIK3CA*-mutant tumors and patients without detectable *PIK3CA*-mutant tumors will be randomized separately using a permuted-block randomization method.

Randomization will be stratified by the following criteria:

- Visceral versus non-visceral disease
 - Visceral disease: Metastatic disease in the lung, liver, adrenal glands, brain, heart, pericardium, pleura, peritoneum, or other end-organs of the chest, abdomen, and pelvis
 - Non-visceral disease: Absence of metastatic disease in visceral organs. Pleural effusions, ascites, disease involving lymph nodes, and disease involving bone are not considered to be visceral disease.

- Sensitivity versus non-sensitivity to the patient's most recently administered endocrine therapy
 - Sensitive to most recently administered endocrine therapy (fulfilling either of the criteria below):
 - For patients with no endocrine treatment in the advanced or metastatic setting, at least 24 months of adjuvant endocrine therapy prior to disease recurrence
 - Documented clinical benefit (CR, PR, or SD \geq 24 weeks) to most recent endocrine treatment in the advanced or metastatic treatment setting
 - Non-sensitive: not satisfying criteria listed as sensitive
- Geographical region:
 - Western Europe, United States, Canada, Australia
 - Asia
 - Rest of World (remaining countries)

The iDMC, the independent statistical group (an independent vendor) facilitating the iDMC meetings, and the Sponsor-independent PK bioanalytical personnel will be unblinded to the treatment assignment. The study team will be unblinded at the time when the iDMC recommends to stop the trial and the Sponsor decides to stop the trial or at the time of the final PFS analysis if the study is not stopped early. Investigators and patients will remain blinded to individual patient-level treatment assignment until *approximately the end of August 2018, at which time unblinding is permitted at the discretion of the investigator or Sponsor.*

Although PK samples must be collected from patients assigned to the comparator arm to maintain the blinding of treatment assignment, PK assay results for these patients are generally not needed for the safe conduct or proper interpretation of this trial. Sponsor personnel responsible for performing PK assays will be unblinded to patients' treatment assignments to identify appropriate PK samples to be analyzed. Samples from patients assigned to the comparator arm will not be analyzed except by request (i.e., to evaluate a possible error in dosing).

Until approximately the end of August 2018, if unblinding is necessary for patient management (e.g., in the case of a serious adverse event for which patient management might be affected by knowledge of treatment assignment), the investigator will be able to break the treatment code by contacting the IxRS. Treatment codes should not be broken except in emergency situations. If the investigator wishes to know the identity of the study drug for any other reason, he or she should contact the Medical Monitor directly. The investigator should document and provide an explanation for any premature unblinding (e.g., accidental unblinding or unblinding due to a serious adverse event).

For regulatory reporting purposes, and if required by local health authorities, the Sponsor will break the treatment code for all serious, unexpected suspected adverse reactions (see Section 5.7) that are considered by the investigator or the Sponsor to be related to study drug.

4.3 STUDY TREATMENT

4.3.1 Formulation, Packaging, and Handling

4.3.1.1 Taselisib

The taselisib tablet is a white to off-white, film-coated, immediate-release formulation of 2 mg strength.

4.3.1.2 Fulvestrant

Fulvestrant will be supplied by the Sponsor per country-specific requirements. For countries in which the Sponsor is supplying fulvestrant, it will be supplied in sterile, single-patient, prefilled syringes containing 50 mg/mL fulvestrant, as a 5-mL injection. For details regarding storage of fulvestrant, refer to the fulvestrant package insert or SmPC.

4.3.2 Dosage, Administration, and Compliance

4.3.2.1 Taselisib

The taselisib 4-mg dose will be taken orally once a day (4 mg PO QD). Taselisib is formulated as 2-mg tablets, so patients will take two 2-mg tablets daily to receive a 4-mg dose. Taselisib will be administered in the clinic at Cycle 1, Day 1 and Cycle 1 Day 15 and on each subsequent day that a cycle visit is scheduled, after the predose assessments and procedures, and after the fulvestrant administration (except for Cycle 2 Day 15). Taselisib will be administered at home on all non-clinic visit days. Patients should take the taselisib dose at the same approximate time each day without regard to the timing of administration of food. If a dose is missed (not taken within 6 hours after the scheduled dosing time), the patient should resume dosing with the next scheduled dose. Missed or vomited doses will not be made up. For additional details, see [Appendix 1](#).

Guidelines for dosage modification and treatment interruption or discontinuation are provided in Section 5.1.1.1.

4.3.2.2 Placebo

The taselisib placebo (corresponding to 4-mg dose) dosage will be supplied as 2 tablets PO QD. Taselisib placebo will be administered in the clinic at Cycle 1, Day 1 and Cycle 1, Day 15 and on each subsequent day that a cycle visit is scheduled, after the predose assessments and procedures, and after the fulvestrant administration (except for Cycle 2, Day 15). Taselisib placebo will be administered at home on all non-clinic visit days. Taselisib placebo should be taken at the same approximate time each day without regard to the timing of administration of food. If a dose is missed (not taken within 6 hours after the scheduled dosing time), the patient should resume dosing with the next

scheduled dose. Missed or vomited doses will not be made up. For additional details, see [Appendix 1](#).

4.3.2.3 Fulvestrant

Fulvestrant 500 mg will be administered in the clinic (before administration of taselisib/placebo) as two IM injections of 250 mg each at Cycle 1, Days 1 and 15 and Day 1 of each subsequent 28-day cycle. For details regarding the dosing instructions and safety profile of fulvestrant, refer to the fulvestrant package insert or SmPC.

The fulvestrant dose level cannot be modified. In general, the investigator may consider continuing fulvestrant if the adverse event observed is not thought to be fulvestrant-related. See Section [5.1.2.1](#) for guidelines for treatment interruption or discontinuation of fulvestrant.

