1.4 BACKGROUND ON FULVESTRANT

Fulvestrant is an ER antagonist approved for the treatment of postmenopausal patients with HR+ breast cancer who have disease progression following other anti-estrogen therapy (MedImmune 2013). Fulvestrant binds to the ER, disrupting the signaling pathway, which leads to ER degradation. The recommended dose of fulvestrant is 500 mg given by intramuscular (IM) injection on Days 1, 15, and 29 of the first month, then monthly thereafter. This dose of fulvestrant was confirmed in a randomized clinical study of 250 mg versus 500 mg IM on a monthly basis (Di Leo et al. 2010). Fulvestrant 500 mg given on a monthly basis provided superior clinical benefit (progression-free survival HR=0.80; 95% CI: 0.68, 0.94; p=0.006) compared with a 250-mg dose, but was accompanied by a higher rate of injection-site reactions (Di Leo et al. 2010). This dose of fulvestrant has also shown a trend toward improvement in overall survival compared

with the 250-mg fulvestrant dose (median duration of overall survival [OS] is 26.4 months vs. 22.3 months). The lower dose of fulvestrant (250 mg) is recommended in patients who have liver dysfunction (Child-Pugh Class B disease).

Clinical studies comparing fulvestrant 250 mg given once a month with anastrozole 1 mg daily have demonstrated similar efficacy between the two agents (Osborne et al 2002; Robertson et al. 2009). Similar rates of objective responses (15%–20%), median time to progression (3.4–5.5 months), and duration of OS (25–30 months) were reported and were not statistically different. Similar efficacy (measured by median time to progression) between fulvestrant and exemestane has also been demonstrated in postmenopausal women who had received prior aromatase-inhibitor therapy for advanced breast cancer (Chia et al. 2008).

The common adverse events associated with the use of fulvestrant include injection site pain, nausea, bone pain, arthralgia, headache, back pain, fatigue, extremity pain, hot flashes, vomiting, anorexia, asthenia, musculoskeletal pain, cough, dyspnea, and constipation. Increases in liver enzymes (AST, ALT, alkaline phosphatase [ALP]) have also been reported in approximately 15% of patients. In randomized studies that compared fulvestrant with anastrozole, similar rates of common adverse events were reported, with the exception of injection-site pain.

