5.1.1 Management of Selected Toxicities Observed with Taselisib in Clinical Studies

Experience with PI3K inhibitors to date has demonstrated that the agents are generally well-tolerated. Common adverse events seen in ongoing clinical trials that are testing PI3K inhibitors include fatigue, diarrhea, skin rash, altered taste, pneumonitis, and hyperglycemia. In general, these agents appear to be reasonably well-tolerated at doses examined to date without irreversible and/or intolerable toxicities.

The toxicities observed with taselisib are consistent with those observed with other PI3K inhibitors. Selected toxicities of interest for taselisib include gastrointestinal toxicities, pneumonitis, rash, stomatitis, and hyperglycemia. Certain adverse events (e.g., rash, colitis, and pneumonitis) may also occur within 4 weeks of holding or stopping taselisib. On the basis of prior clinical experience with the taselisib and fulvestrant combination, some patients have continued to derive clinical benefit with single-agent fulvestrant even after discontinuation of taselisib. Therefore, in some cases per

investigator assessment, fulvestrant dosing may be continued while taselisib or placebo is being held or discontinued (e.g., for adverse events). The fulvestrant dose level should not be modified.

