5.1.1.1.5 Potential Abnormal Liver Function Tests

Some patients have experienced elevations of liver function test results (e.g., AST or ALT) while receiving taselisib in prior clinical studies. Patients will be monitored throughout the study treatment for changes in liver function tests. Given the potential for hepatic toxicity, all patients must have adequate liver function as manifested by measurements of serum bilirubin and hepatic transaminases for initial and continued dosing. Separate criteria for eligibility are given for patients with hepatic metastases.

For new abnormal liver function test results (e.g., elevated AST or ALT), a standard clinical work-up to understand the etiology of the abnormality should take place per local guidelines. In many cases, elevated liver function test results may be a result of liver metastases, concomitant medications, or biliary obstruction. Dose delay and modification for patients who experience abnormal liver function test results can also follow the guidelines in [Table 8](#) if deemed clinically appropriate by the investigator.

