5.1.2.1 General Guidance for Dose Modifications and Delays for Fulvestrant

The fulvestrant dose level cannot be modified. In general, the investigator may consider continuing fulvestrant if the observed adverse event is not thought to be fulvestrant-related.

If a scheduled dose coincides with a holiday or inclement weather or other conditions that preclude dosing, dosing should commence on the nearest following date, and subsequent dosing can continue on a new 28-day schedule on the basis of the new IM injection date.

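### The fixed fulvestrant dose rule is not reconciled with the lower dose that the protocol itself reports for Child-Pugh Class B liver dysfunction, so no stated rule covers a patient who reaches Class B on study and stays on fulvestrant

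*Combined protocol and SAP*

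**What the plan says.** Section 1.4 of the protocol, in its background on fulvestrant, reports: "The lower dose of fulvestrant (250 mg) is recommended in patients who have liver dysfunction (Child-Pugh Class B disease". This is the only place in the documents where Child-Pugh class is mentioned.

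Section 4.3.2.3, which governs dosing, sets 500 mg given "as two IM injections of 250 mg each at Cycle 1, Days 1 and 15 and Day 1 of each subsequent 28-day cycle". It then says: "For details regarding the dosing instructions and safety profile of fulvestrant, refer to the fulvestrant package insert or SmPC". Its next paragraph opens with "The fulvestrant dose level cannot be modified" and points to Section 5.1.2.1 "for guidelines for treatment interruption or discontinuation of fulvestrant".

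Section 5.1.2.1 repeats the fixed-dose rule and adds that, in general, "the investigator may consider continuing fulvestrant if the observed adverse event is not thought to be fulvestrant-related". Its only other content is what to do when a holiday, bad weather or similar prevents dosing. Section 5.1.1 says: "The fulvestrant dose level should not be modified".

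On liver function, Section 5.1.1.1.5 says: "Given the potential for hepatic toxicity, all patients must have adequate liver function". The sentence goes on to name bilirubin and transaminases as the measures and to apply the requirement both at the start of dosing and as dosing continues. Section 4.6.2 requires study drug to stop for a condition judged to jeopardize the patient's safety, and for unacceptable toxicity.

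**The concern.** The protocol reports one dose as recommended in Class B dysfunction, sends sites to the label for dosing instructions, and forbids any change from a different dose without exception. A site whose patient reaches Class B and is to stay on fulvestrant finds no sentence that tells it how these statements combine.

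The situation can arise. Patients with liver metastases may enter with AST and/or ALT up to 5.0 x ULN (Section 4.1.1). Section 5.1.1.1.5 reports liver test elevations on taselisib and names liver metastases and biliary obstruction among the possible causes. Sections 3.1 and 5.1.1 allow fulvestrant to continue after taselisib or placebo has been stopped for toxicity, so a patient with a liver problem can remain on fulvestrant.

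What is at stake is the safety of those few patients and uniform handling of the background drug across sites. The fixed-dose rule, followed as written, keeps such a patient at a dose level other than the one Section 1.4 reports as recommended. Section 9.2 rules out advance requests to deviate, so a site cannot settle the matter case by case with a waiver.

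**Working it through.** The point rests on no sample size, power, alpha or event figure, so the check is a comparison of texts. The one piece of arithmetic is 2 x 250 mg = 500 mg. The dose reported in Section 1.4 is therefore 250/500 = half the protocol dose, and giving it would be a change of dose level under the fixed-dose rule.

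**Step 1: do the dosing sections agree with each other?** Yes. Sections 4.3.2.3, 5.1.1 and 5.1.2.1 all fix the dose level, and none of them permits 250 mg.

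**Step 2: does Section 1.4 bear on dosing at a site?** Only indirectly. It describes how fulvestrant is recommended in general and gives sites no direction. It gains weight because Section 4.3.2.3 refers sites to the label for dosing instructions. The label is not among the documents, so the recommendation is taken as the protocol reports it.

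**Step 3: does any other section settle the case?**

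| Section | What it offers | What it leaves open |
|---|---|---|
| 4.3.2.3 | Fixed dose; referral to the label; pointer to 5.1.2.1 | Whether protocol or label prevails; no hepatic exception |
| 5.1.2.1 | Continuing after events not thought due to fulvestrant; scheduling delays | No hepatic rule, although it is the section pointed to for interruption and discontinuation |
| 5.1.1.1.5 | Adequate liver function needed at the start and as dosing continues; Table 8 may be used for abnormal liver tests | Placed in the taselisib toxicity section; no threshold for continued dosing; fulvestrant not named |
| Table 8 | Fulvestrant alone may go on after a life-threatening Grade 4 event | Its dose |
| 4.6.2 | Stop for a safety-jeopardizing condition or unacceptable toxicity | Which text governs if fulvestrant continues |

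None of these gives a rule for Class B, and none gives an order of precedence.

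**Step 4: which patients are in scope?** Section 4.1.1 limits bilirubin to 1.5 x ULN (3 mg/dL in documented Gilbert's syndrome) and INR to below 1.5 (a stable INR up to 2.5 on therapeutic anticoagulation). Section 4.1.2 excludes a clinically significant history of liver disease, including cirrhosis. Class B at baseline is therefore unlikely. These criteria apply at entry and do not govern what happens later, so the gap is confined to patients who worsen to Class B on study and remain on fulvestrant. The documents give no number.

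**The case against.** The strongest reply is that the protocol is coherent as it stands. Section 1.4 is background. Every dosing section says the same thing, and the specific fixed-dose sentence in Section 4.3.2.3 naturally takes precedence over the general referral to the label that comes just before it. Section 4.6.2 supplies the safety valve, and continuing fulvestrant is in any case discretionary under Sections 4.3.2.3 and 5.1.2.1. Read together, the design is to give the protocol dose or stop, and a uniform dose keeps background therapy consistent in both arms.

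Much of this stands, and it rules out several stronger readings that a reader might infer.

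- That sites hold two opposite operative instructions. They do not: Section 1.4 does not direct sites, and what the label says about a patient who worsens during treatment cannot be read from these documents.
- That an investigator is forced either to deviate or to dose against the reported recommendation. Stopping is available, and Section 4.6.2 requires it when safety is jeopardized.
- That entry with AST/ALT up to 5.0 x ULN puts many patients at risk of Class B. The documents do not link transaminases to Child-Pugh class.
- That the liver function requirement in Section 5.1.1.1.5 covers only entry. It extends to continued dosing.

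The reply does not close the gap. Give-or-stop is an inference; no section states it for liver dysfunction. Section 5.1.1.1.5 gives no threshold for continued dosing and does not name fulvestrant. Section 4.6.2 depends on a judgement that safety is jeopardized, and is silent on the dosing text when that judgement is not made and fulvestrant continues.

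**Conclusion.** This is an internal inconsistency in clinical management, of low frequency but relevant to safety. The protocol reports a lower recommended dose in Class B dysfunction, refers sites to the label for dosing, forbids any change of dose level, and does not say how these fit together for a patient who develops Class B on study and continues fulvestrant.

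The number of patients is not given and is probably small. Power, type I error and the primary analysis are not affected. Protocol Version 4 was written after the primary PFS analysis, so a change now reaches only patients still receiving fulvestrant.

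The conclusion assumes that Section 1.4 reports the label correctly and that some patients who reach Class B would stay on fulvestrant. If every such patient were stopped under Section 4.6.2, the gap would have no practical effect; the protocol does not say that they would be. Nothing here implies that either dose is the right one.

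**What to change.** Reconcile Sections 1.4, 4.3.2.3, 4.6.2, 5.1.1, 5.1.1.1.5 and 5.1.2.1 so that a single stated rule governs fulvestrant for a patient who develops Child-Pugh Class B dysfunction on study. State whether the protocol or the label prevails where they differ. Put the rule in Section 5.1.2.1, or point to it from there, because that is where Section 4.3.2.3 sends sites. The content of the rule is for the sponsor's clinicians to decide.

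The cost is a few sentences of protocol wording in an amendment, or a site memo. No sample size, analysis or timeline changes.
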